4. BACKGROUND AND RATIONALE

Early rectal cancer can be removed by minimally-invasive surgery, and the standard pathological assessment of the removed tumour gives valuable information about how advanced the tumour is. This information is very important in indicating whether the cancer is likely to recur, and therefore in advising the patient after surgery whether further treatment is advisable, and if not, what is the most appropriate follow-up regime. However there is still a lot of uncertainty in these predictions about recurrence of the cancer, and better tests are being sought. This study aims to look at two further pathology tests, ploidy and stroma ratio in the tumour, and compare these test results with outcome in patients who have had an early rectal cancer removed. This will allow us to assess whether these two tests can give greater accuracy in predicting outcome. If so, we would be better able to advise patients with early rectal cancer about their prognosis and further management.

Routine histopathology analysis of a rectal cancer specimen removed at surgery includes assessment of tumour size, depth of invasion, vascular, lymphatic and perineural invasion, tumour involvement of resection margins and nodal involvement. This information is valuable in predicting outcome. For example, predicted rates of local recurrence at 36 months following local excision of rectal cancer by transanal endoscopic microsurgery (TEM) based on tumour size, depth of invasion and lymphatic invasion have been tabulated [1]. However such models are not perfect, and leave room for improvement. Ploidy and stroma ratio are two further tests which have shown some promise in predicting outcome.

Ploidy refers to the number of sets of chromosomes in a cell nucleus. Most human cells are normally diploid, with two sets of 23 chromosomes. Abnormal tumour cells may have a different number of sets of chromosomes, or be aneuploid, having some replicated or deleted chromosomes. In general, aneuploidy in cancer cells is associated with a worse prognosis. An early study of DNA ploidy in rectal cancer using flow cytometry showed an independent but small predictive effect of aneuploidy on survival [2]. Technological advances now allow more accurate and detailed assessment of ploidy. The DNA ploidy status of tumour cells in early ovarian cancer has been found to predict which patients will

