5. OBJECTIVES AND OUTCOME MEASURES

Objectives	Outcome Measures	Timepoint(s) of evaluation of this outcome measure (if applicable)
Primary Objective To compare results of [A] ploidy and [B] stroma analysis with outcome after surgery to remove early rectal cancer	Correlation between [A] ploidy status and [B] tumour: stroma ratio with local recurrence of cancer	Time between surgery for rectal cancer and local recurrence
Secondary Objectives To compare results of ploidy and stroma analysis with survival after surgery to remove early rectal cancer To assess predictive value of [A] ploidy and [B] stroma analysis for outcome after surgery to remove early rectal cancer To compare results of [A] ploidy and [B] stroma analysis with outcomes by use of adjuvant treatment	Correlation between [A] ploidy and [B] stroma analysis with overall survival after TEM surgery to remove rectal cancer Contribution of [A] ploidy and [B] stroma analysis to a regression model for local recurrence after TEM surgery to remove rectal cancer Subgroup analysis comparing [A] ploidy and [B] stroma results with local recurrence and survival for patients who did and did not receive adjuvant chemo- or radiotherapy	Time between surgery for rectal cancer and death

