8.5. Data Handling

For Group A patients, who gave consent at the time of surgery, a member of the care team will extract the relevant data, including tumour characteristics, any (neo-)adjuvant treatment details and outcome information, identified only by MRN, from the TEM database. The care team member will then securely transfer this anonymised data, identifiable by MRN only, to the research team. The research team will then allocate each participant a study ID according to the recruitment log, and replace the MRN with the unique study ID. The transfer will be done using a password protected spreadsheet sent via encrypted email. For all other patients, who sign a specific study consent form, the researcher will prepare the data extract from the TEM database, identified only by MRN, and then replace the MRN with a study ID. The researcher will securely provide a list of MRNs, with date of surgery, to the pathology department. The MRNs will be linked to a unique study ID in a separate recruitment log.

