9.1. Description of Statistical Methods

All data will be stored in an Excel worksheet and analysed using Excel and R (a statistical programme).

The DNA ploidy results and tumour: stroma ratio will be correlated with local recurrence and survival. A subgroup analysis will additionally correlate ploidy and stroma with local recurrence and survival with and without adjuvant treatment.

A regression model will be developed incorporating ploidy and tumour: stroma ratio, along with a number of other known prognostic factors that are routinely collected, to assess whether ploidy and stroma have independent prognostic value in determining length of survival free of local recurrence, and length of disease-free survival.

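### Secondary outcome ii promises predictive value, but the regression tests only independent prognostic value with no measure of contribution, and the no-imputation rule clashes with full inclusion if any covariate is incomplete

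*Combined protocol and SAP*

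**What the plan says.** Section 4 states the purpose: "This will allow us to assess whether these two tests can give greater accuracy in predicting outcome". Sections 2 and 5 make it a secondary objective: "To assess predictive value of [A] ploidy and [B] stroma analysis for outcome after surgery to remove early rectal cancer". The matching outcome measure, repeated in section 9.3, is how much each marker contributes to a local-recurrence regression. No statistic is attached to the word *contribution*.

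Section 9.1 describes that regression. It takes in the two markers "along with a number of other known prognostic factors that are routinely collected, to assess whether ploidy and stroma have independent prognostic value", and continues "in determining length of survival free of local recurrence, and length of disease-free survival". Section 9.4 sets a general 0.05 level.

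The covariates are not listed. Section 4 says that routine histopathology "includes assessment of tumour size, depth of invasion, vascular, lymphatic and perineural invasion, tumour involvement of resection margins and nodal involvement", and that recurrence rates after TEM "based on tumour size, depth of invasion and lymphatic invasion have been tabulated". Both are background; neither is adopted as the model.

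The endpoint is not settled. For local recurrence, section 5 gives "Time between surgery for rectal cancer and local recurrence", while section 9.1 models a recurrence-free survival time, and no section says how a death without recurrence is treated. Section 9.1 also models disease-free survival, which is not an outcome measure in section 5 or 9.3; those list overall survival.

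On missing data, section 9.5 uses what is available and excludes imputation. Sections 9.3 and 9.6 put all participants into the analysis, apart from those who withdraw consent.

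**The concern.** Two different questions are being treated as one. Whether a marker keeps an association with outcome after adjustment is a question about a coefficient. Whether it improves prediction is a question about how well a model performs with it and without it. Section 4 wants the second, so that patients can be given better advice after surgery; section 9.1 describes the first. A marker can pass the first test and add almost nothing to the second, so a significant result could be read as evidence that the test is useful when that has not been examined.

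The missing-data point is narrower. Standard regression software omits any patient who lacks a model covariate. If there are such patients, a default fit cannot satisfy both section 9.5 and section 9.6, and some of what may be few recurrences would be lost.

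**Working it through.** **1. The plan's own figure.** Section 9.2 justifies 150 patients by the size of similar studies and by feasibility. It gives no effect size, power or event rate, so 150 cannot be reproduced and event counts must be assumed.

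- Local recurrence 10-20% (assumption): 150 × 0.10 = 15 to 150 × 0.20 = 30 events.
- Three tabulated TEM factors plus two markers, 5 terms: 15/5 = 3 to 30/5 = 6 events per parameter.
- All seven routine items in section 4 plus two markers, 9 terms (illustration only): 15/9 = 1.7 to 30/9 = 3.3.
- If deaths without recurrence also count (a further 10-20%, assumption): 150 × 0.20 = 30 to 150 × 0.40 = 60 events, or 6 to 12 per parameter with 5 terms. Under these assumptions the endpoint definition alone doubles the event count.

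**2. Association is not accuracy.** In a simple illustration (one simulated set of 6,000 for each hazard ratio, so the last digit is noisy; base linear predictor SD 1, marker prevalence 40%, 15% events), an independent hazard ratio (HR) of 1.5 moved the C-index from 0.758 to 0.759, and an HR of 2.0 from 0.752 to 0.768.

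At the study's size, the assumptions were: size N(0,1); depth in three levels at 40/35/25%; lymphatic invasion 15%; ploidy positive 50%; stroma N(0,1); latent correlation 0.3 among factors and 0.1 with and between markers; exponential times; follow-up uniform over 1.5-9.5 years. Weak base factors had HR 1.2 (size, per SD), 1.2 (depth, per level) and 1.5 (lymphatic); strong ones 1.5, 1.6 and 2.5. Modest markers had HR 1.5 (ploidy) and 1.2 (stroma, per SD). With 2,000 datasets per row, Cox models with both markers added gave:

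| Base factors | Events | Joint test significant | Of these, true C-index gain below 0.01 |
|---|---|---|---|
| Weak | 15 | 15.6% | 33% |
| Weak | 30 | 25.8% | 27% |
| Strong | 15 | 15.9% | 89% |
| Strong | 30 | 27.8% | 88% |

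**3. The adjusted test itself.** With null markers and a fixed 5-term model, the likelihood-ratio test rejected in 5.7-7.2% of 4,000 datasets per scenario (SE at most 0.44 points). That is modestly above 5%.

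**4. Why an added accuracy figure needs correction.** With null markers and 5 terms, the apparent C-index gain at 15/30 events was 0.035/0.023 (weak) and 0.021/0.011 (strong), although the true change was negative (-0.009 to -0.018). Bootstrap correction (300 datasets, 60 resamples), corrected against true gain:

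| Markers, base factors | 15 events | 30 events |
|---|---|---|
| Null, weak | +0.007 vs -0.010 | +0.002 vs -0.009 |
| Null, strong | -0.006 vs -0.018 | -0.008 vs -0.012 |
| Real, weak | 0.050 vs 0.051 | 0.058 vs 0.060 |
| Real, strong | 0.023 vs 0.015 | 0.025 vs 0.022 |

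Here real markers are HR 2.0 (ploidy) and 1.41 (stroma, per SD). For null markers the error left, by subtraction in the table, is 0.004-0.011 at 30 events and 0.012-0.017 at 15. With imputation as well (120 datasets, 5 imputations, 30 resamples), real markers gave 0.024 against 0.024 at 30 events, but 0.028 against 0.012 at 15. All these gains are for both markers together; single-marker gains were not simulated.

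**5. Missing covariates.** With a share m missing independently in each of k covariates, the share of patients lost is 1 - (1 - m)^k. For k = 3 and m = 2-5% (assumption): 1 - 0.98³ = 5.9% (9 of 150) to 1 - 0.95³ = 14.3% (21 of 150). If the gaps fall in the same patients, the loss is 2-5% (3 to 8).

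Power of the 2-df Wald test at m = 5%, missing completely at random, strong base factors, real markers (400 datasets, 10 imputations, SE at most 2.5 points):

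| Gaps | Events | Complete data | Complete-case | Imputed |
|---|---|---|---|---|
| Independent | 30 | 64.2% | 55.5% | 63.5% |
| Independent | 15 | 27.3% | 23.3% | 27.5% |
| Clustered | 30 | 64.2% | 62.7% | 64.2% |
| Clustered | 15 | 27.3% | 26.3% | 28.0% |

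Type I error with imputation was 4.3-4.8%.

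**The case against.** *Contribution* could well mean comparing models with and without the markers, and the sentence about accuracy is rationale rather than an objective. Part of this stands: the plan does not exclude such a comparison. But predictive value is a stated objective in sections 2 and 5, the measure is undefined, and the only purpose that section 9.1 gives the model is independent prognostic value.

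Nothing in the plan says that patients will be dropped. That stands. It is an inference from default software behaviour; a missing-category indicator is another possibility. The factors are routinely collected and come from one pathology assessment, so gaps may be rare or clustered. In the clustered case the power difference is only 1.5 to 1.7 points (64.2 - 62.7 and 28.0 - 26.3).

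The plan promises no accuracy figure, so optimism in the C-index is not a fault of the plan. That also stands. It bears only on the form that an added measure should take.

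From section 9.7, which treats deviation reporting as not applicable, a reader might infer that covariates chosen after seeing the data would go unrecorded. The documents do not support this: choosing covariates under an open list is not a deviation, and section 12.4 requires a final report.

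**Conclusion.** The point holds for secondary outcome ii and the plan should be changed. The predictive-value objective has no analysis that measures prediction, and this rests on the text alone. How often a significant result would come with negligible gain depends on assumptions: 27-33% or 88-89% in the cases tried, according to the strength of the base factors. All event rates, effect sizes and missingness here are assumed, because the documents give none.

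The conflict between section 9.5 and sections 9.3 and 9.6 is conditional on incomplete covariates. Its cost runs from almost nothing to about 8 points of power (63.5% against 55.5%) under the least favourable pattern tried.

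A reader might infer that the regression is invalid or that the primary result is at risk. Neither follows. The adjusted association test is usable, and the primary correlation with local recurrence does not depend on this model.

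**What to change.** 1. **Section 9.1.** Fix in advance a small base model from factors already collected, for example the tumour's size, its depth and lymphatic invasion. Use one stated local-recurrence endpoint and say how deaths without recurrence are handled. Add ploidy and tumour:stroma ratio, with coding fixed in advance, each separately and then together, because the objectives ask about [A] and [B] individually and a joint result would not show which marker contributes. Report adjusted hazard ratios with 95% confidence intervals for each marker. Define contribution as the bootstrap optimism-corrected change in C-index for each marker and for both, and state that the correction is incomplete if recurrences are very few (about 15). Reconcile disease-free survival with the outcome measures in sections 5 and 9.3.
2. **Section 9.5.** Replace the blanket rule for the regression: if covariates are incomplete, they are multiply imputed, with outcome and markers in the imputation model; marker results are not imputed. Complete-case analysis is a sensitivity analysis.
3. **Sections 9.3 and 9.6.** State that marker analyses include all consenting patients with a usable marker result, and report the number without one. The eligibility criteria already require a usable tissue sample, so this mainly concerns failed assays.

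No new patients or assays are needed: section 8.5 describes the data extract as "including tumour characteristics, any (neo-)adjuvant treatment details and outcome information". The cost is wording, a little more R code, a missing-at-random assumption and a less favourable accuracy figure than an uncorrected one. If covariates are nearly complete, imputation changes little.

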9.2. The Number of Participants

The study will recruit 150 participants, including both those who have already had surgery since 2007 and new patients having surgery after the study commences. Similar studies using these techniques of ploidy and stroma analysis compared to outcome after colorectal, breast and ovarian cancer that have produced significant results have generally used between around 150 and 300 patients [ref 3-6]. We expect to be able to recruit 150 patients, from amongst both those who have already had surgery and new patients, within a reasonable time-frame of 18 months.

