2. SYNOPSIS

Study Title	An observational study to correlate the results of ploidy and stroma analysis with prognosis in early rectal cancer	
Internal ref. no. (or short title)	Ploidy and stroma in early rectal cancer	
Study Design	Observational study	
Study Participants	Rectal cancer patients	
Planned Sample Size	150 patients	
Follow up duration	Minimum 18 months	
Planned Study Period	2 years	
	Objectives	Outcome Measures
Primary	To compare results of [A] ploidy and [B] stroma analysis with outcome after surgery to remove early rectal cancer	Correlation between [A] ploidy status and [B] tumour: stroma ratio with local recurrence of cancer
Secondary	
To compare results of [A] ploidy and [B] stroma analysis with survival after surgery to remove early rectal cancer
 
To assess predictive value of [A] ploidy and [B] stroma analysis for outcome after surgery to remove early rectal cancer
 
To compare results of [A] ploidy and [B] stroma analysis with outcomes by use of adjuvant treatment
	
Correlation between [A] ploidy and [B] stroma analysis with overall survival after TEM surgery to remove rectal cancer
 
Contribution of [A] ploidy and [B] stroma analysis to a regression model for local recurrence after TEM surgery to remove rectal cancer
 
Subgroup analysis comparing [A] ploidy and [B] stroma results with local recurrence and survival for patients who did and did not receive adjuvant chemo- or radiotherapy

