6. STUDY DESIGN

An observational study to correlate the results of ploidy and stroma analysis with prognosis in early rectal cancer

IRAS reference: 195159 REC reference: 16/WM/0443

CONFIDENTIAL

Date and version No: 21 October 2016 v1.1

Page 6 of 16

This is an observational study comparing results of two specialised pathology tests with outcome after surgical removal of early rectal cancer. No extra interventions will be carried out on patients.

Over 170 patients have already had an early rectal cancer removed by minimally-invasive surgery (transanal endoscopic microsurgery or TEM) since 2007 in Oxford, and more operations take place each month. Data about the tumour and follow-up on these patients is routinely collected in the Oxford TEM database to ensure that patients receive the appropriate investigations and management after surgery, and that any recurrence of the tumour is promptly detected and treated.

For patients who agree to take part in this study, or who consented to donation of tissue for research at the time of surgery, we will perform the extra pathology tests on the tissue which is stored in the Oxford pathology department as standard practice, and compare the test results with the outcome information contained in the TEM database.

The extra pathology tests will be undertaken in a specialist department in Oslo, Norway. The study will involve sending a small section of the preserved tissue from each consenting patient to Norway for analysis. After analysis, any residual parts of the samples will be returned to the Oxford pathology department.

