8. STUDY PROCEDURES

8.1. Recruitment

All patients who have undergone TEM surgery to remove a rectal cancer since 2007 are eligible, as well as new patients having surgery over the study period. Data on these patients is recorded as standard practice in the Oxford TEM database. There will be different groups, according to the time of surgery and whether or not potential participants consented for tissue donation, requiring different identification and recruitment strategies.

Already had surgery groups

Screening: A member of the care team will extract a list of patients who have had TEM surgery for rectal cancer since 2007 from the TEM database, identified by MRN (OUH medical records number) only. The care team member will then screen the casenotes for these patients to determine whether or not they consented to donation of tissue for research on the surgical consent form.

- Group A: Those who already consented for tissue donation

The majority of potential participants signed a donation of tissue for research statement at the time of surgery. If this statement has been agreed to, patients will be considered to have consented to participate in the study. The care team member will pass the list of MRNs (and linked anonymized data) for these patients to the researcher.

- Groups B & C: Those who did not consent to tissue donation at the time of surgery

Once these have been identified, the care team member will identify whether these patients are still undergoing follow-up at Oxford hospitals. For those who are undergoing follow-up (Group B) the member of the care team will provide the researcher with the MRN and date of the next follow-up appointment. For those who are no longer under follow-up (Group C), the member of the care team will post an information sheet and consent form to the potential participant.

For Group B the researcher will contact the patient during their follow-up visit and give them an information sheet about the study. They will be invited to sign a consent form if they wish to participate. Group C will receive an information sheet and consent form through the post, and will be provided with a telephone number should they wish to discuss the study further.

New patients who have not yet had surgery (Group D)

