New patients, who have not yet had surgery, will be identified at colorectal cancer multi-disciplinary meetings. This will involve reviewing the clinical, histological and radiological investigations with other surgeons, oncologists, radiologists and pathologists as part of the normal clinical review process. Patients who are deemed suitable for TEM surgery will be considered eligible. Identified potential participants will then be approached by an investigator, who is a member of their direct care team, during their routine pre-operative clinic visit. They will be provided with an information sheet and given time to ask questions. Patients agreeing to participate will be recruited on their subsequent visit for surgery.

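### The 18-month minimum follow-up is not secured for new (Group D) patients by 18 months of recruitment in a 2-year study, and no outcome cut-off is stated

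*Combined protocol and SAP*

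**What the plan says.** - **Follow-up and calendar.** The synopsis (Section 2) gives follow-up as "Minimum 18 months", without limiting it to any group, and a planned study period of 2 years.
- **Recruitment.** Section 9.2 expects to reach 150 from already-operated patients "and new patients, within a reasonable time-frame of 18 months". Section 8.1 makes patients operated on since 2007 eligible, "as well as new patients having surgery over the study period". Of Group D it says: "Patients agreeing to participate will be recruited on their subsequent visit for surgery". Section 8.3 also lets them sign at the pre-operative clinic. Either way, they enter at or shortly before surgery.
- **Clock.** Section 5 gives the timepoint of the primary outcome as "Time between surgery for rectal cancer and local recurrence". Survival is likewise timed from surgery.
- **Source of outcomes.** Section 6 will "compare the test results with the outcome information contained in the TEM database". For patients who sign a study consent form, Section 8.5 says "the researcher will prepare the data extract from the TEM database"; it gives no date for that extract or for the Group A extract.
- **End of study.** Section 8.8 ties this to the last laboratory result from Oslo, not to any follow-up milestone.
- **Analysis set.** Section 9.6 includes every consenting patient, with no follow-up threshold.

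**The concern.** Three planning figures are stated in different places: 18 months of recruitment, at least 18 months of follow-up, and 2 years in all. For patients whose clock starts at surgery during recruitment, the first two add up to more than the third. Nothing else in the plan closes the gap. There is no last surgery date for Group D, no censoring or extract date, and no rule that keeps patients with short follow-up out of the analysis.

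What is at stake is mainly the truth of a stated design property. A reader of the synopsis would take it that every analysed patient had been followed for at least 18 months for local recurrence. On the natural reading of the calendar, some would not have been. A second consequence is that an unstated cut-off leaves the extract date open to choice after results begin to be seen.

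**Working it through.** **Inputs.** Minimum follow-up 18 months and study period 24 months (synopsis); recruitment 18 months and N = 150 (Section 9.2); clock starts at surgery (Section 5).

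**Assumptions.** Outcomes are read at month 24; month 0 is the start of both the study and recruitment; Group D surgery is spread evenly up to month R. None of these is stated in the documents.

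**1. Does the plan's 2 years follow from its own parts?** Time needed = recruitment + minimum follow-up = 18 + 18 = 36 months. The plan gives 24, a gap of 12 months for the last new patient.

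**2. Follow-up at month 24 for surgery at month t** = 24 − t. Reaching 18 months requires t ≤ 24 − 18 = 6. At t = 18, follow-up is 24 − 18 = 6 months.

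**3. Dependence on when Group D surgery ends.** Shortest follow-up = 24 − R; share of Group D below 18 months = (R − 6)/R.

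| Last Group D surgery (R) | Shortest follow-up | Share of Group D short |
|---|---|---|
| month 6 | 18 months | 0 |
| month 12 | 12 months | 6/12 = 1/2 |
| month 18 | 6 months | 12/18 = 2/3 |
| month 24 | 0 months | 18/24 = 3/4 |

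The last row is included because Section 8.1 sets no end to new surgery before the study ends.

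**4. Size among the 150, for R = 18.** Group D's size is not stated, so it is varied.

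| Group D | Short (× 2/3) | Share of 150 |
|---|---|---|
| 0 | 0 | 0% |
| 15 | 10 | 7% |
| 30 | 20 | 13% |
| 50 | 33 | 22% |
| 75 | 50 | 33% |

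To judge which rows are plausible: Section 6 says "Over 170 patients have already had an early rectal cancer removed by minimally-invasive surgery" since 2007. Taking 170 cases over about 9.8 years (January 2007, assumed, to the October 2016 protocol) gives 170/117.6 = 1.446 a month. Over 18 months with full consent that is 1.446 × 18 = 26 new patients, of whom 1.446 × 12 = 17 would be short (12% of 150). This is a rough guide and not a ceiling: the count is a minimum, and the current rate may differ from the average.

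**5. Already-operated patients (Groups A to C).** Surgery was before month 0, so at least 24 months have passed by month 24. The calendar limit does not touch them.

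**6. Information lost, for R = 18.** Among the short patients, the shortfall runs evenly from 0 to 12 months, a mean of 6. Past cases, if spread evenly since January 2007, have on average 117.6/2 + 24 = 82.8 months of potential follow-up; Group D has 24 − 9 = 15.

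- Group D = 15: 10 × 6 = 60 patient-months short, out of 135 × 82.8 + 15 × 15 = 11,403, or 0.5%.
- Group D = 30: 20 × 6 = 120 patient-months short, out of 120 × 82.8 + 30 × 15 = 10,386, or 1.2%.

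The denominators ignore deaths and loss to follow-up, so the true percentages would be somewhat higher. The order of size is what matters.

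**The case against.** The strongest reply is that the conflict is conditional. Nothing says that outcomes are read at month 24. They come from a routine clinical database that keeps running, and the end of study is a laboratory event. An extract taken 18 months after the last surgery would satisfy the synopsis. Recruitment might also finish early, or Group D might be small or empty, since more than 170 past cases are available for 150 places.

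This stands as far as it goes: the plan cannot be said to breach its own minimum for certain. But it does not commit to a later extract, to an early close of Group D, or to any cut-off at all. A 2-year study period makes month 24 the natural reading. The 18 months is therefore stated but not secured.

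A reader might also infer that the primary analysis will count short-follow-up patients as recurrence-free, because Section 9.1 says only that the tests will be correlated with recurrence. The documents do not support going that far. Section 5 frames the primary outcome as a time from surgery, and the regression in Section 9.1 concerns how long patients survive without local recurrence. If a plain yes/no comparison were used, follow-up would already differ by years across a cohort operated on since 2007. That is a separate question about an unnamed method and does not come from this calendar.

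**Conclusion.** The point holds in a conditional form and is minor. If outcomes are read at the end of the 2 years, Group D patients operated on after month 6 have less than the stated 18 months, down to 6 months for surgery at month 18 and lower if surgery continues beyond that. With even accrual to month 18, about two thirds of Group D are short: 10 of 15 or 20 of 30, which is 7% or 13% of 150. Already-operated patients are outside the problem.

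The effect on a time-to-event analysis is small, because these patients are censored early and not misclassified; about 1% of potential follow-up is lost at those sizes. What needs correcting is a stated minimum that would be untrue for part of the analysed cohort, together with the missing cut-off that would settle the matter.

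The result rests on a month-24 read-out, a common start for study and recruitment, and even accrual. A reader might infer that month 24 is the planned cut-off, or that a firm upper limit can be put on the number affected. The documents support neither: they give no cut-off, no Group D number and no accrual rate.

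**What to change.** State one outcome cut-off for all groups, take the final TEM database extract at that date, and name a last surgery date for Group D. Then choose one of two routes.

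1. **Keep the 2 years and restate the minimum by group (preferred, cheapest).** Give 18 months or more for already-operated patients. For Group D, give 24 minus the month of the last included surgery, which is 6 months if recruitment runs to month 18. The cost is wording in the synopsis and Sections 8.5, 8.8 and 9.2, and a less favourable stated minimum.
2. **Keep 18 months for everyone and move the cut-off** to 18 months after the last included surgery: month 18 + 18 = 36 if recruitment ends at month 18. The cost is a calendar up to 12 months longer. The later extract relies on linkage by medical record number, so it must be reconciled with the statement in Section 10.3 that investigators hold and access personal data for under three months. The longer study may also need amendment approval under Section 12.3.

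Under either route, the synopsis and Sections 8.1, 8.8 and 9.2 should give one consistent calendar, fixed before test results are compared with outcomes.
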